1. PROTOCOL SUMMARY

Title	A Transformative Approach Utilizing Behavioral Economics, Education, and Data Science to Support Patients Initiating PrEP with Retention-in-care and Medication Adherence and Persistence
Funder	ViiV Healthcare
Study Design	Observational Cohort Study
Study Population	Patients >18 y/o who are newly started on PrEP at WVHR and have access to a smart phone with data.
Study Size	n = 105 (70 CAB-LA injection participants and 35 oral PrEP participants)

Study Duration	12 months
Study Site(s)	West Virginia Health Right
Intervention Description	Participants will have been prescribed CAB-LA, daily FTC/TDF, or daily FTC/TAF in accordance with the WVHR standard of care by a licensed HCP prior to enrolling in the study. Those receiving CAB-LA will be in one arm and those receiving oral PrEP will be in the other arm of the study.
Study Aim	To determine the persistence of injectable PrEP compared to oral PrEP
Primary Objectives	To evaluate medication persistence in patients receiving CAB-LA injections vs oral PrEP and who engage with a digital health companion program
Secondary Objective 1	Evaluate retention-in-care in patients receiving CAB-LA vs oral PrEP
Secondary Objective 2	Evaluate PROs (including PrEP medication satisfaction, PrEP acceptance, PrEP-Related Stigma, and reasons for PrEP discontinuation) in patients receiving CAB-LA vs oral PrEP
Secondary Objective 3	Evaluate the acceptability, appropriateness, and helpfulness of a digital health companion program for PrEP
Secondary Objective 4	Evaluate the acceptability, barriers to, and facilitators for implementation of CAB-LA PrEP

2. INTRODUCTION

2.1. Background

2.1.1. Numerous studies have found that medication persistence with oral PrEP (defined as continued use of PrEP over time) tends to be short, with many patients discontinuing oral PrEP within about 6-12 months. Moreover, PrEP persistence has been found to be shorter among underserved populations with health inequities—including Medicaid patients, patients in rural areas, transgender patients, and Black and Latinx patients. The introduction of long-acting, injectable cabotegravir (CAB-LA) for PrEP is viewed by many as an opportunity to overcome adherence

challenges. Moreover, based on its administration by a healthcare professional (HCP) every two months, the implementation for CAB-LA in real-world settings affords HCPs new opportunities to engage with patients, especially those with high unmet needs, which may influence PrEP persistence, retention-in-care, and patient-reported outcomes (PROs). To support adoption of CAB-LA for HIV PrEP, real-world studies are urgently needed to evaluate the impact of CAB-LA on outcomes that are critical to successful HIV prevention, such as adherence, persistence, retention-in-care, and PROs. Additionally, given its mode of administration, studies are needed to elucidate barriers to as well as facilitators for the implementation of CAB-LA PrEP in clinical settings. For people living with HIV, findings from the CUSTOMIZE study shed light on patient and provider perspectives on implementation of CAB+RPV LA for treatment of HIV. These insights from diverse settings of HIV treatment can serve as a springboard for evidence generation on the real-world use of CAB-LA for PrEP. Recognizing the need to support clinics in implementing and streamlining the delivery of PrEP, PRIME recently partnered with West Virginia Health Right (WVHR) in an implementation science initiative. Through this initiative, significant advances were made in overcoming barriers related to PrEP access. Specifically, the initiative directly resulted in a landmark decision by the Director of the West Virginia Medicaid program to remove all prior authorization requirements for CAB-LA for PrEP after attending the PRIME program. Building on this momentum and reduced barriers to CAB-LA access in WV, we propose to evaluate the implementation of CAB-LA supported by a novel PrEP mobile health app among underserved populations receiving care at WVHR. WVHR is a 501(c)3 non-profit, patient-centered, medical home that provides comprehensive primary and specialty care to >40,000 uninsured, underinsured, and underserved adults. Among services provided, WVHR provides HIV prevention care, harm reduction services, behavioral health care, and transgender health care—which is the only transgender health program in the region. Its in-house pharmacy fills >90,000 prescriptions annually,

including access to free medications for uninsured patients. Additionally, WVHR utilizes a mobile health clinic to care for hard-to-reach populations. WVHR is in Kanawha County, which is designated by the CDC as one of the top vulnerable areas of rapid spread of HIV due to injection drug use. Due to its location, services provided, and focus on uninsured/underinsured individuals, the populations cared for by WVHR encompass those with high unmet needs and PrEP-related disparities, including women, persons who inject drugs (PWID), transgender persons, persons in rural areas, and persons with low-income. Importantly, WVHR is committed to sustaining the HIV prevention initiative after the proposed study has concluded, as stated in the letter from Chief Executive Officer, [name], DNP, APRN, BC, FNP

2.2. Study Rationale

2.2.1. The digital health companion intervention that will be utilized in this research project is based on combining the principles of behavioral health economics, patient education, and data science to drive positive behavior change in PrEP adherence, persistence and retention-in-care. Prior research supports the acceptability and effectiveness of mobile health interventions for adherence to oral PrEP. For example, a PrEP adherence mobile app (“Dot”), which was tailored for culturally-diverse MSM, was found to have high user acceptability and resulted in increased adherence to daily PrEP over the 6-week intervention. Other mobile interventions have similarly been found to be effective in supporting PrEP adherence in key populations, including in MSM (PrEPmate, Viral combat) and cisgender women (AEGiS/iTAB). Importantly, surveys show that 86% of Medicaid beneficiaries own smartphones and that approximately one-quarter to one-half use their smartphone for a variety of health purposes, such as filling prescriptions, measuring health goals, monitoring health issues, and receiving reminders about prescription drugs. Thus, there is an important opportunity to evaluate mobile health interventions for PrEP among low-income, Medicaid populations, and to expand the use of mobile interventions for supporting persistence to long-acting injectable PrEP.

2.3. Hypothesis

2.3.1. This study is designed to test the hypothesis that, compared to oral PrEP, use of CAB-LA in underserved populations in a real-world setting supported by a digital health companion program will be associated with greater medication adherence, persistence, retention-in-care, and improved PROs.

3. STUDY OBJECTIVES

3.1. Study Goal

3.1.1. The study will evaluate the extent to which real-world use of CAB-LA for PrEP in underserved populations impacts PrEP adherence, persistence, retention-in-care, and PROs compared with oral PrEP. Additionally, the study will examine implementation of a digital health companion program that leverages education and behavioral economics to support patients on PrEP, and assess clinician perspectives as well as barriers to, and facilitators for implementation of CAB-LA in a patient-centered medical home.

3.2. Primary Objective

3.2.1. To evaluate medication adherence and persistence in patients receiving CAB-LA vs oral PrEP and who engage with a digital health companion program

3.3. Secondary Objectives

3.3.1. Evaluate retention-in-care in patients receiving CAB-LA vs oral PrEP

3.3.2. Evaluate PROs (including PrEP Medication Satisfaction, PrEP Acceptance, PrEP-Related Stigma, and reasons for PrEP discontinuation) in patients receiving CAB-LA vs oral PrEP

3.3.3. Evaluate the acceptability, appropriateness, and helpfulness of a digital health companion program for PrEP

[figure not shown]
3.3.4. Evaluate the acceptability, barriers to, and facilitators for implementation of CAB-LA

4. STUDY DESIGN

4.1. Study Design

4.1.1. The research project follows a hybrid effectiveness-implementation research design, with the primary aim focused on evaluation of PrEP adherence, persistence and retention-in-care with CAB-LA compared with oral PrEP, and secondary aims focused on evaluating patient-reported outcomes (PROs), implementation of a digital health intervention to support adherence and persistence, and evaluating contextual factors around implementation of CAB-LA. The project is in the initial implementation stage, with CAB-LA beginning to be rolled out at WVHR after the recent state Medicaid decision to drop prior authorization requirements for CAB-LA. The proposed study will utilize a digital health intervention with behavioral health economics and patient education from PRIME and Reciprocity to evaluate the adoption and implementation for PrEP adherence and persistence. The implementation aims of the study will leverage the RE-AIM framework as follows: Assessment of the digital health intervention will focus primarily on individual-level dimensions of RE-AIM, including reach and effectiveness. For example, in assessing reach of the digital health intervention, participant demographics will be compared to the intended audience to evaluate the extent to which populations with high unmet needs were engaged. Conversely, assessment of the implementation of CAB-LA will focus on system-level dimensions of RE-AIM, such as qualitative assessments of barriers to and facilitators for implementation of CAB-LA. Furthermore, evaluation of implementation outcomes will be based on the Proctor et al. conceptual framework, using specific measures developed by Weiner et al. to assess acceptability, appropriateness, and feasibility of the intervention. In addition, evaluation of PROs will be informed by a review of validated instruments, including HIVSTQ (HIV Treatment Satisfaction Questionnaire), SMSQ (Study Medication Satisfaction Questionnaire), I-TAQ (Injection Treatment Acceptance Questionnaire), ACCEPT (Chronic Treatment Acceptance Questionnaire), and the PrEP Stigma Scale, with survey items tailored to evaluate PrEP acceptance, satisfaction, and perceptions of PrEP-related stigma for both the CAB-LA and oral PrEP arms.

4.2. Study Schema

5. STUDY POPULATION

5.1. Inclusion Criteria

5.1.1. >18 y/o

5.1.2. Initiation of PrEP with CAB-LA, daily FTC/TDF, or daily FTC/TAF prescribed in accordance with the WVHR standard of care practices (based practices on CDC PrEP 2021 Clinical Practice Guidelines) by a licensed HCP

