5.2.2. Receiving HIV PrEP care outside of WVHR

5.2.3. Positive HIV diagnosis

5.2.4. Contraindication to oral or injectable PrEP therapy

5.2.5. Receiving oral bridging therapy prior to injectable PrEP therapy

5.2.6. Confirmed pregnancy

5.2.7. Vulnerable populations

5.3. Study Sample

5.3.1. n = 105 (70 CAB-LA intervention participants vs 35 oral PrEP participants)

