6.5. Switching between PrEP regimens

6.5.1. To be included in final data analysis, participants cannot switch between PrEP regimens before 6-months duration of initial PrEP.

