6.10. Possible Participant Pathways

6.10.1. There will only be two observational cohort arms. Patients will either be placed into the injectable PrEP arm or the oral PrEP arm based on their baseline prescription.

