Appendix B: CAB-LA PrEP Arm Instruments

Activity Title: Baseline Information About You

Activity Description: Today we'll ask you to answer some questions about yourself. The survey is 17 questions and should take about 10 minutes to complete.

Baseline Demographic Survey

Question	Question #
What year were you born? [Write in]	1
Which of the following best describes your racial/ethnic background? (Select all that apply) 
  African American/Black  Asian/Pacific Islander  Caucasian/White  Hispanic/Latinx  Native American/Alaska Native  A race or ethnicity not listed: [Write in] 	2
How do you describe your gender? (Select 1) 
  Female  Male  Transgender woman  Transgender man  Non-binary  A gender not listed: [Write in] 	3
How do you describe your sexual orientation? (Select 1) 
  Heterosexual/Straight  Gay or Lesbian  Bisexual  Queer or Sexually Fluid  Pansexual  A sexual orientation not listed: [Write in] 	4
What is the highest degree or school level you have completed? (Select 1) 
  Primary school  Some high school  High school diploma or GED  Some college  2-year college degree  4-year college degree  Graduate level degree  A school level not listed: [Write in] 	5
What health coverage are you currently enrolled with? (Select up to 2) 
  Medicaid  Medicare  Affordable Care Act 	6

 Uninsured  Private health insurance  A health coverage not listed: [Write in]	

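### PrEP initiation has no look-back and prior PrEP use is not a named baseline item or covariate, so an imbalance in PrEP experience could confound the persistence and adherence comparisons

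*Combined protocol and SAP*

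**What the plan says.** The study title and the Protocol Summary concern people starting PrEP. The summary's population is "Patients >18 y/o who are newly started on PrEP at WVHR and have access to a smart phone with data", and Appendix G (Study Schema) says nearly the same. The operative criterion, 5.1.2, is "Initiation of PrEP with CAB-LA, daily FTC/TDF, or daily FTC/TAF prescribed in accordance with the WVHR standard of care practices". Neither place says whether this means never used PrEP, not used it for a stated time, or not had it prescribed at this clinic.

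Two exclusions come close to the question. Section 5.2.2 excludes "Receiving HIV PrEP care outside of WVHR", and 5.2.5 excludes "Receiving oral bridging therapy prior to injectable PrEP therapy". Section 6.5.1 requires, for the final analysis, that "participants cannot switch between PrEP regimens before 6-months duration of initial PrEP". Arms follow the prescription at entry (6.10.1): "Patients will either be placed into the injectable PrEP arm or the oral PrEP arm based on their baseline prescription".

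The baseline survey has the same 17 topics in Appendix B (CAB-LA) and Appendix C (oral). Its only PrEP question asks why the person is using it. Section 7 compares unspecified demographic and clinical variables at baseline and takes into multivariate models those associated with the outcome on univariate analysis. The tests for persistence and adherence themselves are unadjusted.

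**The concern.** Previous PrEP experience is likely to predict persistence. Section 2.1.1 says that many people stop oral PrEP within about 6 to 12 months. Someone who has already passed that period has shown that they can stay on PrEP; someone returning after stopping has shown the opposite. Either kind of patient may differ from a true first-time user, whatever regimen they now take.

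In a randomised trial such differences would balance on average. Here the regimen is chosen by patient and clinician (6.9.1), so PrEP history could influence both the arm and the outcome. If the shares of experienced users differ between arms, part of any observed difference belongs to history and not to the regimen. A larger sample would not remove this. As the plan stands, the imbalance would not appear in the survey-based baseline table, and no named covariate would adjust for it.

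**Working it through.** **1. Does any criterion close the gap?**
- 5.1.2 and the Protocol Summary: initiation and new start are undefined.
- 5.2.2: written in the present tense, so it covers current care elsewhere, not past use elsewhere.
- 5.2.5: limited to bridging. In 6.2.3.1 and 6.2.6.1 bridging means oral cover for patients on the injection pathway, not an earlier oral regimen.
- 6.5.1: limits switching before 6 months of the first regimen, but does not say whether PrEP taken before enrolment counts.
- 6.10.1: assigns the arm by entry prescription, not by history.

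So a person who used PrEP in the past and restarts, or who transfers from another provider, is not clearly excluded from either arm.

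**2. Is history recorded anywhere in the plan?** It is not in the survey of either arm. A baseline evaluation is scheduled (6.1, 6.2), but its contents are not listed. The EHR (Study Outcomes Table), the WVHR pharmacy (5.1.3) and claims (6.2.3.1, 6.2.4.1) are available sources. No section assigns them to PrEP history.

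**3. The plan's own figure.** The Sample Size paragraph assumes adherence of 0.90 (n = 70) and 0.65 (n = 35).

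SE = √(0.90 × 0.10/70 + 0.65 × 0.35/35) = 0.0882

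0.25 ± 1.96 × 0.0882 = 0.0771 to 0.4229, half-width 0.173

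This matches the stated interval, so there is no arithmetic error. The interval describes sampling error only and makes no allowance for confounding.

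**4. Illustrative size of the confounding.** The documents do not give the share of experienced users or their persistence. I assume no regimen effect, end-of-study persistence of 0.65 in new users and 0.85 in experienced users. With experienced shares f_C (CAB-LA) and f_O (oral):

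spurious difference = (f_C − f_O) × (0.85 − 0.65)

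| f_C − f_O | Spurious difference |
|---|---|
| 0.20 | 0.20 × 0.20 = 0.04 |
| 0.50 | 0.50 × 0.20 = 0.10 |
| −0.20 | −0.04 |
| −0.50 | −0.10 |

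Only the gap between the arms matters for the bias; equal shares give none. If experienced users persist less well than new users, every sign reverses.

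**5. Effect on the test.** I enumerated the uncorrected chi-square test exactly for 70 against 35, two-sided at 5%, with f_O = 0. The false-positive rate is 5.1% with no imbalance, 7.3% at f_C = 0.20 and 19.7% at f_C = 0.50. With 0.90 in place of 0.85 for experienced users, it is 10.5% at f_C = 0.25 (bias 0.25 × 0.25 = 0.0625) and 28.8% at f_C = 0.50 (bias 0.50 × 0.25 = 0.125).

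**6. Precision of an analysis limited to people without recent PrEP.** Using the plan's 0.90 and 0.65:

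| CAB-LA n | Oral n | Half-width |
|---|---|---|
| 70 | 35 | 0.173 |
| 56 | 35 | 0.176 |
| 35 | 35 | 0.187 |
| 56 | 28 | 0.193 |

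The loss is modest, and it is larger when the smaller oral arm also shrinks.

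**The case against.** The wording can fairly be read more strictly. What is initiated in 5.1.2 is PrEP, with CAB-LA as one means, so an established oral user who moves to injections is not initiating PrEP. The protocol has a separate term, switching, for that event (6.5.1), and clinicians verify eligibility (5.4.1). This stands: the fault is an undefined term, not a permission to enrol switchers.

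A reader might go further and infer a one-sided leak favouring CAB-LA, because Section 4.1 describes the site "with CAB-LA beginning to be rolled out at WVHR after the recent state Medicaid decision" and existing oral users might move across. The documents do not support that. One criterion governs both arms, and the inference needs a loose reading for CAB-LA and a strict one for oral PrEP. Returners and transfers can enter either arm, and nothing describes a pool of oral users expected to change.

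A reader might also conclude that the imbalance could never be detected. That is too strong: pharmacy, EHR and claims data could show earlier use at WVHR. What remains is that no section plans to use them for this, and PrEP obtained elsewhere may be missed.

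Finally, it is tempting to set the 4 to 10 points against the 25-point difference in the Sample Size paragraph. That difference is for adherence; no persistence difference is planned.

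**Conclusion.** The point holds as a gap in design and data collection. Initiation has no look-back, and prior PrEP use is neither asked at baseline nor named as a baseline variable or covariate. In a non-randomised comparison tested without adjustment, an imbalance in PrEP experience would confound both persistence and adherence.

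Whether an imbalance will arise, which arm it would favour and how large it would be cannot be determined from the documents. The 4 to 10 points of spurious persistence difference rest wholly on the assumed 65% and 85% rates, no regimen effect, and an assumed gap of 20 to 50 percentage points in the experienced share. They show that the issue is large enough to merit a question at entry, not that the result will be biased by that amount.

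**What to change.** - Add one month-0 item to the baseline surveys in Appendices B and C: any past PrEP use, type, and when last used. Cross-check the answer against WVHR pharmacy and EHR records.
- In Section 7, name this variable in the baseline comparison and prespecify it as a covariate in the persistence and adherence models, so that its inclusion does not depend on univariate screening.
- Prespecify a supporting analysis in participants with no recent PrEP use, for example none in the 6 months before month 0.
- State in 5.1.2 what initiation means, and in 6.5.1 whether PrEP taken before enrolment counts towards the first regimen.

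Restricting entry by a look-back is optional. It would narrow a cohort meant to reflect routine practice and might slow accrual; recording history and analysing by it meets the concern without that.

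The cost is one extra survey question and, in the supporting analysis, a somewhat wider interval. The item should be in place before the first participant enters, because PrEP obtained outside WVHR cannot be reliably reconstructed later.

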5.1.3. PrEP dispensed by WVHR pharmacy

5.1.4. Access to a smart phone

5.2. Exclusion Criteria

5.2.1. <18 y/o

5.2.2. Receiving HIV PrEP care outside of WVHR

5.2.3. Positive HIV diagnosis

5.2.4. Contraindication to oral or injectable PrEP therapy

5.2.5. Receiving oral bridging therapy prior to injectable PrEP therapy

5.2.6. Confirmed pregnancy

5.2.7. Vulnerable populations

5.3. Study Sample

5.3.1. n = 105 (70 CAB-LA intervention participants vs 35 oral PrEP participants)

5.4. Screening and Enrollment

5.4.1. Patients will be enrolled on a rolling basis via HCPs at WVHR. HCPs will verify participant's eligibility for the study.

6. STUDY INTERVENTIONS AND PROCEDURES

6.1. Study Procedures and Interventions Table (Figure 6a)

CAB-LA PrEP Arm (N=70)													
Month 0	Month 0	Month 1	Month 2	Month 3	Month 4	Month 5	Month 6	Month 7	Month 8	Month 9	Month 10	Month 11	Month 12
Baseline labs and 1 st PrEP injection Baseline demographic survey	Baseline evaluation and introduction to support group	2 nd PrEP injection Persistence Assessment PRO data collection – Set #1	Education modules and health literacy evaluation	Follow-up labs and 3 rd PrEP injection PRO data collection – Set #2 Persistence Assessment	Education modules and health literacy evaluation	Follow-up labs and 4 th PrEP injection Persistence Assessment PRO data collection – Set #1	Education modules and health literacy evaluation	Follow-up labs and 5 th PrEP injection Persistence Assessment	Education modules and health literacy evaluation	Follow-up labs and 6 th PrEP injection PRO data collection – Set #2 Persistence Assessment	Education modules and health literacy evaluation	Follow-up labs and 7 th PrEP injection Persistence Assessment PRO data collection – Set #1	PRO data collection – Set #2
Oral PrEP Arm (N=35)													
Month 0	Month 0	Month 1	Month 2	Month 3	Month 4	Month 5	Month 6	Month 7	Month 8	Month 9	Month 10	Month 11	Month 12
Baseline labs and PrEP prescription filled Baseline demographic survey	Baseline evaluation and introduction to support group	Persistence Assessment PRO data collection – Set #1	Education modules and health literacy evaluation Persistence Assessment	Follow-up labs and PrEP prescription refill PRO data collection – Set #2 Persistence Assessment	Education modules and health literacy evaluation Persistence Assessment	Persistence Assessment PRO data collection – Set #1	Follow-up labs and PrEP prescription refill Education modules and health literacy evaluation Persistence Assessment	Persistence Assessment	Education modules and health literacy evaluation Persistence Assessment	Follow-up labs and PrEP prescription refill PRO data collection – Set #2 Persistence Assessment	Education modules and health literacy evaluation Persistence Assessment	Persistence Assessment PRO data collection – Set #1	Follow-up labs and PrEP prescription refill PRO data collection – Set #2 Persistence Assessment
Reciprocity App – Education Modules 
 Month 2: PrEP Medicines Month 4: Protecting Yourself from HIV, STIs, and other infections Month 6: Building a Support System for HIV Prevention Month 8: Being an Active Participant in Your Own Care Month 10: Overcoming Stigma and Becoming a Health Advocate 						Persistence assessment: patient self-report & barriers/challenges							
						PRO data collection (Set #1): 
 PrEP Medication Satisfaction PrEP-Related Stigma AIM 		PRO data collection (Set #2): 
 PrEP Acceptance IAM 					

